1.1.4 REPORTING EVENTS TO PARTICIPANTS

If a safety event experienced by a participant during the trial's conduct provides new safety information involving potential significant risk to current and future participants, participants will be notified of the safety event in compliance with CSP standard operating procedures.

1.1.5 EVENTS OF SPECIAL INTEREST

The following Events of Special Concern will be reported by the Safety Management Team in accordance with CSP standard operating procedures: suicide, a death due to unusual circumstances, a medical error, an overdose of the study drug, or when a participant is responsible for another person's death, great bodily harm, or significant property damage.

1.1.6 REPORTING OF PREGNANCY

As a strategy to mitigate risk to any pregnant or breastfeeding woman, participants who are pregnant or breastfeeding at time of randomization will be followed for any safety outcomes until the end of study participation. Appropriate transition of care will take place at the end of the study in the event any serious adverse events occurred. Sites will notify the Chair's Office and the CSPCC and CSPCRPCC as soon as they become aware of any participant who becomes pregnant during the study, collection of safety data will continue until the end of participation.

1.2 UNANTICIPATED PROBLEMS

1.2.1 DEFINITION OF UNANTICIPATED PROBLEMS (UP)

The Office for Human Research Protections (OHRP) considers unanticipated problems involving risks to participants or others to include, in general, any incident, experience, or outcome that meets all of the following criteria:

- Unexpected in terms of nature, severity, or frequency given (a) the research procedures that are described in the protocol-related documents, such as the IRB-approved research protocol and informed consent document; and (b) the characteristics of the participant population being studied;
- Related or possibly related to participation in the research (“possibly related” means there is a reasonable possibility that the incident, experience, or outcome may have been caused by the procedures involved in the research); and
- Suggests that the research places participants or others at a greater risk of harm (including physical, psychological, economic, or social harm) than was previously known or recognized.

1.2.2 UNANTICIPATED PROBLEM REPORTING

Serious Unanticipated Problems require prompt reporting. The Sponsor must be notified within 72 hours of the site investigator becoming aware of the event. Sites will report Ups to the VA Central IRB in accordance with VA CIRB requirements and timeframes, as detailed on the VA CIRB website.

1.2.3 REPORTING UNANTICIPATED PROBLEMS TO PARTICIPANTS

Participants will be informed of any important new information that may affect their safety or their willingness to participate.

2 STATISTICAL CONSIDERATIONS

2.1 STATISTICAL HYPOTHESES

The primary null hypothesis tests whether the proportion of death or respiratory failure by Day 28 differs between the experimental arm (convalescent plasma) and the control arm (saline). The key secondary null hypothesis tests whether time to recovery differs between the experimental and control arms.

2.2 SAMPLE SIZE DETERMINATION

Primary endpoint

The Chi-square test will be used to compare treatment arms on the proportion of death from any cause or respiratory failure up to and including Day 28, with two-sided significance level = 0.05.

A meta-analysis of studies of SARS coronavirus infection and severe influenza reported that convalescent plasma led to an absolute reduction in the risk of mortality from 7% to 23% and a 54% greater likelihood of discharge by day 22²⁵. These data suggest that the treatment benefit of convalescent plasma in reducing the risk of death and respiratory failure may be substantial, particularly early in hospitalization. For this trial we conservatively assume a 10% absolute reduction (30% in the control group and 20% in the convalescent plasma group) given that this trial allows local standard of care in both arms, which may include effective medications for COVID-19.

Table 6. Required number of participants to have 80%, 85% or 90% power for the primary outcome, assuming no missing data.

Proportion in the control group	Absolute reduction	Corresponding proportion in the plasma group	Number of participants needed		
			80% power	85% power	90% power
35%	11%	24%	532	610	712
	10%	25%	652	746	874
	9%	26%	858	976	1134
	8%	27%	1042	1192	1396
30%	11%	19%	474	542	634
	10%	20%	582	666	778
	9%	21%	730	834	976
	8%	22%	936	1072	1254
25%	11%	14%	400	458	536
	10%	15%	496	566	662
	9%	16%	624	714	836
	8%	17%	806	922	1080

Table 6 provides the total number of participants needed for 80%, 85% or 90% power to detect a range of differences in the primary outcome, using the z-test with a two-sided significance level = 0.05 and assuming no missing data. A total of 666 participants are needed to have 85% power for a 10% absolute reduction when the proportion of death or respiratory failure is 30% in the control group (**Table 6**). This sample size has 76% power to detect a 9% absolute reduction

when the control rate is 30% and has 90% (81%) power to detect a 10% absolute reduction when the control rate is 25% (35%) (**Table 7**).

Table 7. Power of a study of 666 participants to detect differences in the primary outcome, assuming no missing data.

Proportion in the control group	Absolute reduction	Corresponding proportion in the convalescent plasma group	Power
35%	11%	24%	88%
	10%	25%	81%
	9%	26%	72%
	8%	27%	61%
30%	11%	19%	91%
	10%	20%	85%
	9%	21%	76%
	8%	22%	66%
25%	11%	14%	95%
	10%	15%	90%
	9%	16%	83%
	8%	17%	72%

We do not plan to inflate the target number of events for the planned interim analysis described in **Section 9.4.6** below. The planned early stopping boundaries are conservative and the impact on power is negligible: the power with 666 participants (with no missing data) is 84.0%.

Assuming 5% of participants have missing data on primary outcome (such as due to lost of follow-up or early withdrawal from the study), we plan to randomize **702** ($=702/0.95$) participants.

Key secondary endpoint

The key secondary endpoint is time to recovery up to and including Day 28. Currently there is limited information about the anticipated effect size or the proportion of participants who will recover by Day 28. A preliminary review of data from ACCT-1 demonstrated a recovery rate ratio of 1.312.

Table 8 gives the power of the study for time to recovery in a study of sample size 702, for a range of treatment to control recovery rate ratio and proportion of recovery by day 28. If approximately 70% of study participants recover by Day 28, a study of 702 participants will have 83% power to detect a recovery rate ratio of 1.3.

Table 8. Power for time to recovery for a study of 702 participants

Recovery rate ratio	Overall proportion of recovery by day 28			
	80%	75%	70%	65%
1.20	58%	55%	52%	49%
1.25	75%	73%	70%	66%
1.30	87%	85%	83%	80%
1.35	94%	93%	91%	89%
1.40	98%	97%	96%	95%

Number of sites and recruitment period

Based on CDW data, there were over 3000 Veterans admitted to VA Medical Centers for SARS-CoV-2 infections in January-April 2020, and 40-50% of them had respiratory failure or death within 28 days of hospital admission. In March-May 2020, the top 25 VA Medical Centers had on average 29 (median = 24) hospital admissions per month. Conservatively, assuming each participating site can randomize on average 2 participants per month, the target sample size 702 can be achieved by 15 months of recruitment at 25 sites. We estimate up to 2000 patients may be screened before enrollment and up to 1500 patients enrolled/consented in order to have 702 randomizations.

2.3 POPULATIONS FOR ANALYSES

The primary analysis will be based on an intention-to-treat population, including all participants randomized. The safety analysis will be based on a modified intent-to-treat population consisting of all participants who received at least one dose of any study intervention.

2.4 STATISTICAL ANALYSES

2.4.1 GENERAL APPROACH

This is a double-blind controlled randomized trial testing a superiority hypothesis of convalescent plasma versus saline with a two-sided type I error rate of 5%. Secondary hypotheses have been ordered according to relative importance, with one key secondary hypothesis highlighted. These will be described according to the appropriate summary statistics (e.g., proportions for categorical data, means with 95% confidence intervals for continuous data, median for time-to-event data).

A statistical analysis plan will be developed prior to unblinding of study and database lock.

2.4.2 ANALYSIS OF THE PRIMARY EFFICACY ENDPOINT(S)

The primary efficacy analysis to compare the proportion of death or respiratory failure by Day 28 will be done by the Chi-square test. Difference in the proportions and the 95% confidence interval will be presented. To account for randomization stratification factors, site and age (≥ 65 vs < 65 years old), we will use a logistic regression model with site and age as covariates, or as random effects in a generalized linear mixed effects model. We will also perform regression analyses to adjust for baseline patient characteristics (including age, sex, race, Hispanic ethnicity, ABO blood type, BMI, hypertension, chronic lung, heart or kidney diseases, diabetes, immunosuppression). Odds ratios and 95% confidence intervals will be provided.

Every attempt will be made to obtain outcome data for all participants. While we anticipate minimum loss of follow-up in this short follow-up study, small amounts of missing primary outcome data may occur. In such cases, subjects without the primary outcome data will be excluded from the primary analysis. Sensitivity analyses will evaluate the impact of making different assumptions about missing observations and use analysis methods such as multiple imputations. These analyses will be defined in the Statistical Analysis Plan.

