The trial will be conducted in accordance with International Conference on Harmonization Good Clinical Practice (ICH GCP), applicable United States (US) Code of Federal Regulations (CFR), and applicable VA policies, regulations and procedures. The Study Chairs will assure that no deviations from, or changes to the protocol will take place without prior agreement from the funding agency and documented approval from the VA Central Institutional Review Board (CIRB), except where necessary to eliminate an immediate hazard(s) to the trial participants. All personnel involved in the conduct of this study will have completed Human Subjects Protection and ICH GCP Training prior to participation in study activities.

The protocol, informed consent form, recruitment materials, and all participant materials will be submitted to the VA CIRB for review and approval. Approval of both the protocol and the consent form must be obtained before any participant is enrolled. Any amendment to the protocol will require review and approval by the VA CIRB before the changes are implemented to the study. All changes to the consent form will be VA CIRB approved; a determination will be made regarding whether a new consent needs to be obtained from participants who provided consent using a previously approved consent form.

EXECUTIVE SUMMARY

The very acute onset and rapid dissemination of SARS-CoV-2 (SARS-CoV-2) across the world over several months precluded the early availability of effective preventive and therapeutic interventions. The impact of SARS-CoV-2 is substantial with hospitalization of about 20% of those infected, half of whom require intensive care due to respiratory failure from which death may ensue. Prominent among those who preferentially experience this high incidence of morbidity and mortality are men over age 65 years with underlying comorbidities such as hypertension, diabetes, lung, heart, kidney or liver disease, obesity and immunocompromise^{1, 2}, clinical features commonly shared by the Veteran population. Effective therapies are currently quite limited. We propose to bolster immune defense against the virus with convalescent plasma that contributes antiviral antibodies and, potentially, non-antibody factors to its therapeutic activity.

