2.2 BACKGROUND

Purpose of the Study

The newly emergent coronavirus SARS-CoV-2 has exceeded two earlier highly fatal species—severe acute respiratory syndrome coronavirus (SARS-CoV) in 2003 and Middle East respiratory syndrome coronavirus (MERS) in 2012 in the speed and breadth of its transmission worldwide and four common upper respiratory coronavirus species in its virulence and associated mortality. Described initially in Wuhan, China, the infection has already spread to infect over 25 million persons worldwide with 860,000 deaths as of September 1, 2020, and over 6 million infected in the U.S. and approaching 200,000 deaths. Although the majority of persons infected recover naturally based on their own innate and adaptive immune responses, up to 20% are ultimately hospitalized with an increased risk of respiratory failure and death. Persons age 65 years or older represent a minority of infections but comprise the majority of those with complications, hospitalization and death^{1,18}. These outcomes are most prominent among older persons with comorbidities, e.g., chronic lung, cardiac and renal disease, as well

as hypertension, diabetes, obesity and immunosuppression¹⁻², conditions common among veterans.

In the absence of an effective vaccine or other biologic preventive measures, treatment options for those with serious disease are also limited. To date, only one antiviral medication (remdesivir) has shown efficacy to shorten time to recovery but not decrease mortality¹⁶. Multiple medications to limit viral replication, minimize inflammation, modulate immune responses are in broad empiric use and testing¹⁹, but none other has been proven to be effective²⁰⁻²³ and a number have untoward side effects²².

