6.3 MEASURES TO MINIMIZE BIAS: RANDOMIZATION AND BLINDING

6.3.1 RANDOMIZATION

The study will randomize participants in equal probabilities to study treatment arms. Currently there are two study treatment arms: convalescent plasma versus saline. Participants will be randomized in 1:1 ratio to these two arms. If additional arms are added to or dropped from the trial, randomization will proceed with an equal probability to each of the remaining arms. Randomization will be stratified by participating site and by age (≥ 65 vs. < 65 years old).

The IWRS (Interactive Web Response System) will be used by authorized study site personnel to randomize eligible participants. It is an intranet-based application that is hosted behind the VA firewall on a VA server at the CSPCRPCC. It is only accessible on the VA network to authenticated VA personnel. Access to study data is restricted to personnel that have registered in the IWRS and have been authorized by the study team. All communication to or from the IWRS is encrypted using Hypertext Transfer Protocol Secure (HTTPS) and is secured using a VA furnished Secure Sockets Layer (SSL) certificate.

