9.4.6.2 INTERIM EFFICACY AND FUTILITY ANALYSIS

We plan to conduct two interim efficacy analyses of the primary efficacy endpoint at 33% and 67% of total information to allow early stopping of the study when there is sufficient evidence that the convalescent plasma group is superior. The p -family alpha spending function of $p=2.5$ with a one-sided significance level 0.025 will be used as a guide for the DMC (non-binding). The type I error spent at the interim efficacy analysis will depend on the actual information time of the interim analysis according to the alpha spending function. If the study is not stopped at interim, the remaining type I error will be spent at the final analysis of the primary outcome. For example, if the two interim analyses occur at exactly 33% and 67% information time, the efficacy boundaries in the z -scale are -2.947 and -2.401, respectively, and the cumulative type I error spent at the two looks are 0.002 and 0.009, respectively; the remaining type I error 0.041 will be allocated to the final analysis.

Conditional power will be presented as an additional guide to the DMC for futility stopping (non-binding). Conditional power is the probability of obtaining a statistically significant treatment

benefit of convalescent plasma at the end of the study given the data accumulated thus far and assuming a hypothesized treatment effect thereafter. If the conditional power is less than 10% under the original treatment effect assumption (30% vs. 20%), consideration should be given to stopping the trial.

Table 9 gives the operating characteristics of the early stopping boundaries for a study of 666 participants, assuming no missing data, the interim analyses are performed at 33% and 67% information time (222 and 444 participants, respectively), and true proportion of death or respiratory failure is 30% in the control group. When the plasma group also has 30% death or respiratory failure (that is, no difference between the two groups), the study has 5.2% probability of crossing the futility boundary at the first interim analysis and 59% probability of crossing the futility boundary at the second interim analysis. When the plasma group has a 10% absolute reduction as compared to the control group (that is, 30% vs. 20%), the study has 11% probability of crossing the efficacy boundary at the first interim analysis and 41% probability of crossing the efficacy boundary at the second interim analysis.

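### The primary chi-square test and risk-difference interval leave out the site and age strata used to randomize; a stratified test is a small, cheap gain if those strata are prognostic

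*Combined protocol and SAP*

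**What the plan says.** Section 6.3.1: "Randomization will be stratified by participating site and by age", with age split at 65 and 1:1 allocation.

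Section 9.4.2 (printed as 2.4.2 in the body): "The primary efficacy analysis to compare the proportion of death or respiratory failure by Day 28 will be done by the Chi-square test". For the effect estimate: "Difference in the proportions and the 95% confidence interval will be presented". Neither sentence mentions the strata. The section then turns to the stratification factors: "we will use a logistic regression model with site and age as covariates, or as random effects in a generalized linear mixed effects model". That model is an addition to the primary test, it reports odds ratios, and it leaves the choice between fixed and random effects open.

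Section 9.4.1 says "A statistical analysis plan will be developed prior to unblinding of study and database lock". Section 9.4.2 hands only the missing-data analyses to that later plan. The documents contain no CMH test and no stratified risk difference.

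**The concern.** Stratified randomization balances the arms within site and age group, so the difference in proportions varies less from trial to trial than under simple randomization. The chi-square test and the ordinary interval use the simple-randomization variance and so overstate the uncertainty whenever the strata predict outcome. Section 9.4.2 accepts the principle of accounting for the strata, but applies it only to a supporting model on a different scale, not to the test and risk difference that decide the trial.

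What is at stake is efficiency. Type I error is not inflated. If site and age carry no prognostic information, nothing is gained.

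**Working it through.** **Inputs from the documents.** 30% v 20% events, two-sided alpha 0.05, 85% power, 666 evaluable and 702 randomized (Section 9.2); 25 sites (Section 1.1); efficacy boundaries -2.947 and -2.401 (Section 9.4.6.2); 84.0% power with interim looks (Section 9.2).

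**Reproducing the plan.**
- n per arm = (1.960 + 1.036)² × (0.3×0.7 + 0.2×0.8) / 0.10² = 332.2, rounded up to 333; total 666. 666/0.95 = 701.05, so 702 for equal arms.
- SE of the difference = √(0.37/333) = 0.0333. Power = Φ(0.10/0.0333 - 1.960) = 85.1%.
- One-sided spending 0.025·t^2.5 at t = 1/3, 2/3 and 1 gives -2.947, -2.401 and a final -2.030. Power with the looks is 84.1% (plan: 84.0%).

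**Assumptions not in the documents.** Permuted blocks of 4; 60% aged 65 or over; 25 equal sites, so 50 cells (666/50 ≈ 13 participants each at the end, 222/50 ≈ 4 at the first look). Three prognostic strengths: none; age OR 2 with between-site SD 0.3 (logit scale); OR 3 with SD 0.5. What the documents offer is indirect:
- Section 2.2 says that infected persons aged 65 or older "comprise the majority of those with complications, hospitalization and death", but gives no age effect among hospitalized patients on oxygen.
- Section 5.5 reports 69% with the primary endpoint at one centre, and Section 9.2 reports 40-50% across VA centres. On the logit scale, 0.80 - 0.00 = 0.80 to 0.80 - (-0.41) = 1.21. This suggests that site matters, but one centre does not estimate an SD.

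**Statistics compared**, with events a, total events m, plasma participants t, control participants c and size n in each cell:
- CMH: z = Σ(a - mt/n) / √Σ[m·t·(n-m)(n-t) / (n²(n-1))].
- Mantel-Haenszel risk difference: Σw(p_plasma - p_control)/Σw, with w = t·c/n and Sato variance.

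**Fixed design, 666 participants, 40,000 trials per scenario:**

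| Strata | Size, chi-square / CMH | Power, chi-square / CMH | 95% CI half-width (points), unadjusted / MH |
|---|---|---|---|
| Not prognostic | 5.0 / 5.0% | 85.2 / 85.0% | 6.52 / 6.54 |
| OR 2, SD 0.3 | 4.5 / 5.0% | 85.3 / 85.8% | 6.52 / 6.43 |
| OR 3, SD 0.5 | 4.1 / 5.0% | 85.6 / 87.4% | 6.52 / 6.27 |

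The Monte Carlo SE is 0.1 point for size and 0.06 to 0.08 point for the paired power difference. Width changes: 6.54/6.52 = +0.3%, 6.43/6.52 = -1.4%, 6.27/6.52 = -3.8%.

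**Hand check of the last row.** The ratio r = 6.27/6.52 = 0.962 approximates true SE over assumed SE. Chi-square size ≈ 2[1 - Φ(1.96/0.962)] = 4.2%. Since 0.10/0.0333 = 3.00, chi-square power ≈ Φ((3.00 - 1.96)/0.962) = 86.0% and stratified power ≈ Φ(3.00/0.962 - 1.96) = 87.7%. All three agree with the simulation to within about half a point.

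**Sensitivity (20,000 trials each).**
- Unequal sites (size CV 0.6) or blocks of 6: -0.4 point with non-prognostic strata and +1.7 at OR 3.
- OR 4, SD 0.7: chi-square size 3.5%, power +2.7 points, interval 6.4% narrower.
- A separately coded simulation gave -0.3 (none), +1.7 (OR 3, SD 0.5) and +3.0 (OR 3, SD 0.8).

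**With looks at 222, 444 and 666 and the existing boundaries.**
- One-sided error: CMH 0.0247-0.0253 (SE 0.0008), and 0.0235-0.0256 in the sensitivity runs; chi-square 0.0199-0.0249.
- Power: CMH 83.9, 84.9 and 86.5%; chi-square 84.1, 84.2 and 84.5%.
- Efficacy crossing at a 10% reduction, CMH: 0.097-0.109 at look 1 and 0.420-0.443 at look 2 (Table 9: 0.112 and 0.411).
- Participants in one-arm cells, who add nothing to CMH: 3.0%, 0.1% and 0% by look (unequal sites 4.9, 0.9 and 0.3%).
- Mantel-Haenszel coverage at the final look is 94.9-95.0%, and 94.0% in the OR 4 alternative, where the true risk difference varies by site.

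**The case against.** The strongest reply is that nothing is wrong. The chi-square test can only err on the conservative side here, the sample size was built on it, and 666, 702 and 84.0% all reproduce. The amendment history shows that age was added as a stratification factor, and Section 9.4.2 updated for the strata, in the same version. A simple primary test with an adjusted supporting model may therefore be deliberate. All of that stands, and it is why this is a point to consider rather than an error. It does not supply a stratified test or a stratified risk difference, and no section assigns one to the later plan.

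The gain is also conditional. With non-prognostic strata, up to about 0.4 point of power is lost, and efficacy crossing at the first look falls from 0.109 to 0.097 (0.103 to 0.088 with blocks of 6). That stands too.

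Fifty cells may look too sparse, and one could ask for a rule that pools small sites. The simulations hold the error rate near 0.025 without pooling, so a rule driven by accrual is not needed.

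Two limits remain. First, the chi-square look-1 futility probability under no difference came out at 0.037-0.042 against 0.052 in Table 9, so the futility column should be recomputed with the plan's own method. Second, the documents do not say whether an interim look has already taken place.

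**Conclusion.** The point holds. The decisive test and its absolute-difference interval omit the randomization strata. The cost is small: over the three main strengths and the variations in site size and block size, CMH changes power by -0.4 to +1.9 points and interval width by +0.4% to -3.8%. Under stronger assumptions the power gain reaches about 3 points. The chi-square remains valid, with size falling to 4.1% at OR 3 and SD 0.5. These figures depend on the assumed age effect, site variation, age mix and block size, none of which the documents give; their direction depends only on whether site and age are prognostic.

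**What to change.** - Make the primary analysis a CMH test stratified by site and age as randomized, with a Mantel-Haenszel risk difference and 95% interval (Sato variance, which tolerates small cells). Keep the unadjusted chi-square as a sensitivity analysis.
- Use the same stratum definition at both interim looks and at the end, with no pooling rule that depends on numbers randomized. A site added later becomes a new stratum.
- Section 9.4.6.2 says "The type I error spent at the interim efficacy analysis will depend on the actual information time". State that information time remains the fraction of participants with outcome data. The Mantel-Haenszel information fractions were 0.315 and 0.662 against the nominal 0.333 and 0.667.
- In the added logistic model, fit two-level age as a fixed effect; site may be fixed or random. Optionally, add baseline NEWS2, already collected under Section 8.2, to the covariate-adjusted regression.
- If an interim look has already used the chi-square, leave that test decisive and add the stratified test and risk difference as pre-specified supporting analyses.

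Cost: an amendment written blind to comparative data. The Statement of Compliance applies: "Any amendment to the protocol will require review and approval by the VA CIRB". Table 9 and conditional power need a re-check. The simulated error rates suggest that the efficacy boundaries can stay. N is unchanged and no new data are needed.

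### The primary 95% confidence interval is not tied to the group-sequential boundaries, and the final critical value is not stated

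*Combined protocol and SAP*

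**What the plan says.** Section 9.4.2 (printed as 2.4.2) tests the 28-day proportion with death or respiratory failure by chi-square and adds: "Difference in the proportions and the 95% confidence interval will be presented". It names no interval method. Section 9.2 (printed as 2.2) sets the test "with two-sided significance level = 0.05".

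Section 9.4.6.2 plans efficacy looks at 33% and 67% information. A power-family spending function with exponent 2.5, "with a one-sided significance level 0.025 will be used as a guide for the DMC (non-binding"), governs them. For looks at exactly those times, "the efficacy boundaries in the z -scale are -2.947 and -2.401, respectively", with cumulative type I error of 0.002 and 0.009. The section then assigns 0.041 to the final analysis without giving a final critical value.

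No section mentions a repeated, stage-wise or otherwise adjusted interval, or a bias-adjusted estimate. Section 9.4.1 says that a statistical analysis plan will follow before unblinding. What Section 9.4.2 expressly leaves to it is the missing-data sensitivity analyses. Section 9.3 puts everyone randomised in the primary analysis.

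**The concern.** A trial that stops for efficacy has been selected for a large observed difference, so the simple difference overstates the effect on average. A trial that runs to the end is tested against a boundary stricter than 1.96, so an interval built with 1.96 can exclude zero when the test does not reject. The two statements of the final level (two-sided 0.05 in Section 9.2, the unspent remainder in Section 9.4.6.2) leave it unclear which critical value the interval should match.

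The headline effect size and its error bars are at stake. The synopsis allows an effective therapy to become the control arm of a later comparison with an updated sample size, so an inflated estimate could carry forward. By Table 9 an early efficacy stop at the design effect has probability 0.112 + 0.411 = 0.523, so a reporting rule for that case is needed.

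**Working it through.** **Inputs from the protocol.** Assumed risks of "30% in the control group and 20% in the convalescent plasma group"; "A total of 666 participants are needed to have 85% power for a 10% absolute reduction"; "Participants will be randomized in 1:1 ratio to these two arms"; looks at 222 and 444 participants. This gives 111, 222 and 333 per arm.

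**Assumptions.** Pooled z test, unpooled Wald interval, 30% control risk, no missing data, and trials stop whenever an efficacy boundary is crossed. The futility guide is not applied unless stated. Each scenario has 1,000,000 simulated trials.

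**1. The plan's own figures reproduce.**
- Sample size: (1.960 + 1.036)² × (0.3 × 0.7 + 0.2 × 0.8) / 0.10² = 332.2, so 333 per arm and 666 in total.
- Cumulative one-sided spend, 0.025 × t^2.5: 0.0016 at t = 1/3 and 0.0091 at t = 2/3. The boundaries solve to 2.947 and 2.401.
- Simulated efficacy stops at 30% vs 20%: 0.108 and 0.413 (Table 9: 0.112 and 0.411).
- Power with the looks: 83.9%. The protocol says "the power with 666 participants (with no missing data) is 84.0" per cent.

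**2. Final critical value.** Spending the rest of the one-sided 0.025 gives z = 2.030, a nominal two-sided p of 0.0424. A matching final interval is therefore about a 95.8% interval. Testing at 1.96 instead would give one-sided type I error of 2.84%.

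**3. The 0.041.** It equals 0.05 − 0.009, a two-sided total less a one-sided spend. On the one-sided scale the remainder is 0.025 − 0.0091 = 0.0159; on the two-sided scale it is 2 × 0.0159, or about 0.032. Used as a nominal two-sided level, 0.041 gives z = 2.044 and one-sided type I error of 0.0244. That is slightly conservative and does not change the conclusions.

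**4. Estimates and ordinary 95% interval.** Stopping shares are from Table 9; the rest is simulated.

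| True reduction (points) | Look-1 stop: share; mean estimate; coverage | Look-2 stop: share; mean estimate; coverage | Coverage, both looks | Coverage, all trials |
|---|---|---|---|---|
| 5 | 1.7%; 19.7; 0% | 9.8%; 12.0; 80% | 69% | 93.5% |
| 8 | 5.6%; 19.8; 52% | 26.6%; 12.3; 95% | 88% | 93.6% |
| 10 | 11.2%; 19.9; 76% | 41.1%; 12.6; 98% | 93.5% | 94.1% |

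The look-1 mean hardly depends on the truth because the boundary sets a floor. With 30% events in the control group, z = 2.947 at 111 per arm needs an observed difference of about 16.3 points. If the futility guide is also followed, overall coverage at a true 10 points is 93.1%.

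**5. Disagreement at the final analysis** (boundary 2.030). The ordinary interval excludes zero while the test is not significant in 2.4%, 2.6% and 1.7% of all trials at true reductions of 5, 8 and 10 points, and in 0.4% under no effect. Example: 100/333 vs 77/333.
- Difference: 0.3003 − 0.2312 = 0.0691.
- Pooled standard error 0.0342, so z = 2.018 < 2.030: not significant.
- Unpooled standard error 0.0341, so the interval is 0.0691 ± 1.96 × 0.0341, or 0.2 to 13.6 points: it excludes zero.

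**6. What adjusted intervals change.**
- *Stage-wise ordering, look 1.* The only more extreme results are larger first-look z values, so the calculation is the fixed-sample one. For 33/111 vs 13/111 the result is 18.0 points (7.6 to 28.4) both ways when one variance convention is used throughout. Mixing a pooled z with the unpooled standard error gives 17.6 (7.2 to 28.0), which is an artefact and not a correction.
- *Stage-wise ordering, look 2* (67/222 vs 40/222, pooled z). 12.2 (4.3 to 20.0) becomes 11.8 (3.7 to 19.8).
- *Stage-wise ordering, final look* (the example in step 5). The lower limit moves to −0.02 or −0.03 points, depending on the variance convention, and the upper limit to 13.5. Interval and test now agree.
- *Repeated interval* (multipliers 2.947, 2.401, 2.030). Coverage after a look-1 stop becomes about 88%, 96% and 98% at true 5, 8 and 10 points; after look 2, 95%, 99% and 99.6%; over all trials, about 97 to 97.5%. Final-look disagreement at true 10 points falls from 1.7% to 0.1% of trials; what remains comes from the pooled test and unpooled interval.

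**The case against.** A reader might infer that the reported interval generally misses the truth after an early stop. The documents do not support that. At the design effect, look 2 supplies 41 of the 52 percentage points of early stopping, with 98% coverage, and coverage over both looks is 93.5%. The 0% figure belongs to a look-1 stop at a true 5-point reduction, which Table 9 puts at 1.7% of such trials.

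A reader might also infer that the sponsor has chosen an unadjusted interval, or that type I error is inflated. The first is a reading of silence: no method is named and a later analysis plan could supply one. That mitigates only in part, because Section 9.4.2 does not list interval construction among the items it defers. The second does not follow, because Section 9.4.6.2 commits the final analysis to the unspent error; the 2.84% arises only if 1.96 were used. The efficacy boundary is also a non-binding guide, and the interval does not drive the stopping decision.

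The simulated look-1 figures ignore overrun. Section 9.2 assumes 25 sites at 2 participants a month, so about 50 people, 25 per arm, would still be in follow-up at a cut, and Section 9.3 keeps them in the primary analysis. At a true 10 points the look-1 mean then falls to (111 × 19.9 + 25 × 10) / 136 ≈ 18.1 points; simulation gave 18.0, with 78% coverage. The exaggeration shrinks but remains.

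Finally, a stage-wise interval alone would leave a look-1 result unchanged. That objection stands, and the remedy below allows for it.

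**Conclusion.** The point holds as a modest, inexpensive correction. The plan has two efficacy looks, an interval not tied to them, no stated final critical value, and a remaining-error figure that mixes one-sided and two-sided scales.

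Overall coverage is only slightly low, and the final-look contradiction is real but infrequent. The main distortion is in the estimate after an efficacy stop: about double the truth at look 1 and about a quarter too large at look 2 when the true reduction is 10 points. Coverage fails seriously only after look-1 stops or when the true effect is well below 10 points.

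These sizes rest on a Wald interval, a 30% control risk, looks at exactly 1/3 and 2/3 information, stopping whenever an efficacy boundary is crossed, and a final test at 2.030.

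**What to change.** Before unblinding:

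1. In Section 9.4.6.2, state the final critical value implied by the spending function: 2.030 if the looks fall at 1/3 and 2/3 information, recomputed from the actual information times otherwise. Replace 0.041 with a remainder on a single scale (0.0159 one-sided), or give the nominal final level (0.0424 two-sided). Align the two-sided 0.05 in Section 9.2 with this.
2. In Section 9.4.2, report a group-sequential 95% interval that matches the boundaries, and a median-unbiased estimate beside the simple difference. Stage-wise ordering serves for look-2 and final-look results.
3. For a look-1 stop, use a repeated interval with the stage boundary as multiplier, and state in the report that the estimate is expected to be exaggerated.
4. Keep everyone randomised, including after the interim data cut, in the primary analysis, as Section 9.3 requires.

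The cost is wording and standard group-sequential software. Intervals become somewhat wider, and conservative where the repeated form is used. For 33/111 vs 13/111 the repeated interval is 2.4 to 33.7 points, against 7.6 to 28.4 for the ordinary one.
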